## 12.2 Statistical Analysis

A Statistical Analysis Plan (SAP) will be written and locked prior to analysis.

In order for the NeuroSAFE PROOF trial to maintain its recruitment inertia, the NeuroSAFE PROOF trial was transitioned from its feasibility and pilot phases to the fully powered trial (covered in substantial amendment 4.0). As such, all subjects from the 51st patient (inclusive) onwards will be reconsented to the larger RCT. Patients 1-50 were treated as part of the NeuroSAFE PROOF Feasibility Trial, which has reported its primary outcome (recruitment). Full 12-month reports of oncological and functional outcomes from the NeuroSAFE PROOF Feasibility Trial will be analysed as a separate cohort, per the feedback of the NeuroSAFE PROOF Feasibility Trial iDMC. Publication of feasibility trial results will not be before main trial recruitment is completed in order to maintain the equipoise of the clinicians and sites involved in recruitment.

### 12.2.1 Intent to treat population

The intent to treat (ITT) population, which is the primary population for efficacy, is defined as all men who provide written informed consent to receive the treatment.

### 12.2.2 Per protocol population

The per protocol (PP) population, which is the secondary population for efficacy, is defined as all ITT subjects who received the intended treatment and had no major protocol deviation or violation that may confound the assessment of efficacy.

### 12.2.3 Safety population

The safety population is defined as all subjects exposed to the treatment

### 12.2.4 Statistical methods

Primary outcome: Comparison of the unpaired proportions of men who recover erectile function at 12 months allocated to the NeuroSAFE intervention versus the control arm, based on an IIEF-5 score of 21 or more. Statistical significance will be established using 95% confidence intervals calculated using the Wilson method. P-values will be reported. Further planned subgroup and sensitivity analyses will be conducted as detailed in section 7.2.1

The secondary outcome #1 will use similar methods to the primary outcome.

There will be no adjustment of p-values for secondary outcomes for multiple testing. STATA statistical software will be used.

Due to interruption the trial due to COVID pandemic, collection of outcomes at particular time points has been affected, with 3- and 6-month time points being less regimented than anticipated. Prior to data lock, the statistical methods will be

reviewed. It is possible that analysis could use survival analysis of time to event analysis up to 12 months for both analyses, if that would make better use of data from multiple time points.

Statistical methods will be reviewed on analysis of a sample of 20% of all data prior to data lock, after data collection and cleaning.

#### 12.2.5 Handling missing data

Multiple imputation will be used for missing data using chained equations in STATA (Multiple imputation using chained equations: Issues and guidance for practice. Ian R. White, Patrick Royston, and Angela M. Wood. Stat Med. 2011 Feb 20;30(4):377-99.)

For the primary outcome, multiple imputation of the ITT population will be based on all time points of outcome measurement as well all relevant participant covariates will be used. Complete case analysis (all available patient data with no imputation) will be reported alongside as a sensitivity analysis to the ITT analysis.

## 13 DATA MONITORING

### 13.1 Discontinuation of the trial

#### 13.1.1 Trial Discontinuation by the Sponsor

The Sponsor may terminate the trial at any time if the following occur, and the investigator is unable to take corrective action in any of these cases:

- The investigator is non-compliant with the protocol
- The investigator is non-compliant with the regulatory requirements
- The investigator is non-compliant with the principles of Good Clinical Practice as outlined in the Declaration of Helsinki and the Research Governance Framework (version 3.3)
- The CRF completion is inadequate

The independent Data Monitoring Committee (iDMC) will perform a quarterly review of the oncological outcomes reported in NeuroSAFE PROOF to ensure participant safety. The iDMC can meet less frequently post recruitment period. The iDMC can advise the Sponsor to terminate the trial early if the 3 monthly BCR safety measure shows an increased incidence in the NeuroSAFE arm (this would be defined as incidences  $p<0.01$ ).

Salvage treatment should only be started after discussion and agreement at SMDT.

#### 13.1.2 Discontinuation of Trial for an Individual Patient

The criteria for discontinuing the trial in the case on individual patients are:

##### **Inter-current illness**

Any illness, which in the judgment of the investigators would affect the assessments of clinical status to a significant degree

##### **Request by the patient**

It is the patients right to request discontinuation of their participation in the trial. If this request is made, it will be respected and will not affect the patient's ability to receive medical care from the investigators now or in the future.

##### **Discontinuation of attendance at an investigating site**

Efforts should be made to maintain the investigations schedule and continue follow-up, even if patients no longer attend the participating institution.

## 13.2 Quality assurance

In order to ensure the quality of the data collected in the trial, the principal investigator will provide means for data monitoring and QC of the database. Data will be handled according to regulatory requirements and be protected according to EU Law Enforcement Directive EU2016/680 (which is now incorporated into UK GDPR) and the Data Protection Act 2018 as well as local data protection requirements.

NeuroSAFE PROOF collects detailed information on histological surgical margin status for safety and future publication purposes. Descriptions of histological diagnosis can differ between sites due to differing interpretations of histological analyses. In order to ensure standard, consistent reporting in line with quality assurance, we will request anonymised pathology reports to ensure accurate, standardised reporting in the trial database. This will occur across both arms of the trial. These reports will be sent electronically in a secure manner (e.g. an NHS.net account) to the NeuroSAFE clinical trial manager at UCL. The reports will be stored in a secure environment that conforms to NHS Digital's data and protection toolkit. The trial manager will de-identify the reports and assign them a unique identifier before sending them for review by a UCLH pathologist. Findings from this quality assurance review will be collated and discussed with all participating pathologists after the last operation (in either arm) has been completed. The reports will be compared to the UCLH pathology reporting standard operating procedure document.

## 13.3 Assessment of safety

### **Adverse Event Definitions**

#### **Adverse Event**

Any untoward medical occurrence in a subject including occurrences, which are not necessarily caused by or related to the intervention

#### **Adverse Reaction**

Any untoward and unintended response in a subject, which is related to the intervention

#### **Unexpected Adverse Reaction**

An adverse reaction, the nature and severity of which is not consistent with the trial intervention(s)

#### **Serious Adverse Event/Reaction (SAE/SAR)**

Any untoward medical occurrence that:

1. Is a life threatening illness or injury
2. Is a permanent impairment to a body structure or function
3. Is a condition requiring hospitalisation or increased length of existing hospitalisation (except hospitalisation for planned admission unrelated to the intervention, urinary retention requiring catheterisation)

4. Is a condition requiring otherwise unnecessary medical or surgical intervention and which might have led to death or serious deterioration in health had suitable action or intervention not taken place.
5. Led to foetal distress, foetal death or a congenital abnormality or birth defect
6. Might have led to any of the above

### **Suspected Unexpected Serious Adverse Reaction**

All suspected adverse reactions related to the intervention that is both unexpected and serious.

### **Adverse Events Classification**

The definitions used to describe the relationship between the adverse event and the trial interventions are the following:

#### **Unrelated**

An adverse event that is definitely not related to the intervention.

#### **Unlikely**

An adverse event for which an alternative explanation is more likely e.g. concurrent drug(s), concomitant disease(s), and/or the relationship in time suggests that a causal relationship is unlikely.

#### **Possible**

An adverse event that might be due to the intervention. An alternative explanation e.g. concurrent drug(s), concomitant disease(s), is inconclusive. The relationship in time is reasonable; therefore, the causal relationship cannot be excluded.

#### **Probable**

An adverse event that might be due to the intervention. The relationship in time is suggestive (e.g. confirmed by rechallenge). An alternative explanation is less likely e.g. concurrent drug(s), concomitant disease(s).

#### **Very likely**

An adverse event, that is listed as a possible adverse reaction and cannot be reasonably explained by an alternative explanation e.g. concurrent drug(s), concomitant disease(s). The relationship in time is very suggestive (e.g. it is confirmed by de-challenge and re-challenge).

#### **Un-assessable**

It is not possible to assign the reaction to any of the above categories because of insufficient, pending, or contradictory information. Further information is requested in order to lead to an attribution of causality.

## 13.4 SAE Reporting

All serious adverse events (SAEs) must be reported to the NCITA Clinical Trials Unit within 24 hours of the Investigator's knowledge of the event (except for those that are identified in the protocol as not needing immediate reporting) via the appropriate SAE form. The trials unit will notify the main Research Ethics Committee and sponsor within 15 days of the Chief Investigator becoming aware of the event.

Those events arising will be reported on a three-monthly basis to the TMG and TSC/iDMC in a summary format, to include:

[figure not shown]
- The number of serious adverse events in a tabular format laying out the percentages of each type of serious events with an indication as to how many of those are thought to be related to the trial intervention.
- The total number of patients recruited during that same 3-month period and in total.
- Clavien-Dindo classified complications of 3 or more will be anonymised and blinded before being submitted to the TMG for central grading and review of site.

## 13.5 Reporting Requirements

In line with the Health Research Authority guidance on non-CTIMP trials, only reports of SAEs that are listed below will require reporting to the CTU (and subsequently sponsor & ethics):

- **Related** to the trial (i.e. they resulted from the use of the NeuroSAFE technique) and
- **Unexpected** (that is not listed in section 13.7 – Expected Adverse Events)

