## 13.7 Expected Adverse Events

The following are expected adverse events following a radical prostatectomy with their corresponding likelihoods (31-34). These should be recorded in the patient's medical records but do not need an Adverse Event CRF to be submitted. These will be recognised as expected for trial treatment.

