### **Expected adverse events:**

#### **Intra-operative**

Bleeding – (requiring transfusion) - 1%  
Visceral injury requiring laparotomy – 1%  
Vascular injury requiring laparotomy – 1%  
Cardiac event (Myocardial infarction 0.1%, Atrial Fibrillation 1.6%, syncope 1.2%).

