#### **Early post-operative**

Wound related problems; infection (2%), incisional hernia (2%)  
Thromboembolic event (deep vein thrombosis or pulmonary embolus 0.8%)  
Lymphoedema – 1% (higher incidence when eLND performed)  
Anaesthetic problems requiring admission to intensive care unit (2%)  
Gastrointestinal; ileus/damage to bowel requiring temporary colostomy (0.5%)  
Seroma – 1%  
Urethral Stricture – 2%

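### Protocol sections 13.4, 13.5 and 13.7 conflict on which safety events are captured, so the by-arm safety table in SAP 4.5 may be incomplete and, for unlisted SAEs, not comparable between arms

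*Protocol*

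**What the plan says.** Four pieces of text govern which safety events reach the trial.

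- **Protocol 13.4** sets a broad rule: "All serious adverse events (SAEs) must be reported to the NCITA Clinical Trials Unit within 24 hours". It excepts events that the Protocol identifies as not needing immediate reporting. It also requires a three-monthly SAE summary, "with an indication as to how many of those are thought to be related to the trial intervention", and adds that "Clavien-Dindo classified complications of 3 or more will be anonymised and blinded before being submitted to the TMG" for central grading.
- **Protocol 13.5** sets a narrow rule: "only reports of SAEs that are listed below will require reporting to the CTU". Two conditions must both hold. The SAE must be related, explained as meaning that "they resulted from the use of the NeuroSAFE technique", and it must be unexpected, meaning absent from the list in 13.7.
- **Protocol 13.7** says that listed complications go in the medical records but "do not need an Adverse Event CRF to be submitted". The list includes "Visceral injury requiring laparotomy" (1%), vascular injury requiring laparotomy (1%) and anaesthetic problems leading to intensive care (2%).
- **SAP 4.5** will report, by arm, how many participants had any adverse event and any SAE within 90 days of surgery. It will also report how many SAEs were considered possibly related to NeuroSAFE.

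Deaths are recorded whatever their cause (Protocol 13.7.1), so they are outside this point.

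**The concern.** SAP 4.5 compares the arms, so it needs events to be captured by the same rule in both arms and whether or not anyone attributes them to the intervention. Sections 13.5 and 13.7, followed as written, do not secure this, and they fail in two separate ways.

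First, the explanation of relatedness in 13.5 refers to the NeuroSAFE technique. A man in the control arm does not undergo it, so an unlisted SAE in that arm can never qualify, while one in the NeuroSAFE arm can. Attribution there may also be made with the allocation known: section 9.2 says that the surgeon is not blinded, and the Protocol does not say who judges relatedness.

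Second, the waiver in 13.7 removes the obvious form for several of the most serious surgical complications. It does so equally in both arms.

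The intervention adds a modified port incision, extraction of the specimen during the operation with re-docking, and sometimes a secondary resection of the bundle (10.1.2). Nothing in the documents shows that these steps cause harm. The safety table is where a reader would look to find out, and it can only show what was captured.

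**Working it through.** **Step 1. What each rule requires, by class of event**

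| Event | 13.4 | 13.5 | 13.7 | Needed for SAP 4.5 |
|---|---|---|---|---|
| Unlisted SAE, NeuroSAFE arm, attributed to the technique | Report | Report | – | Yes |
| Unlisted SAE, NeuroSAFE arm, not attributed | Report | Not required | – | Yes |
| Unlisted SAE, control arm | Report | Cannot qualify | – | Yes |
| Listed serious complication, either arm | Report unless excepted | Not required | Notes only, no AE CRF | Yes |
| Listed lower-grade event, either arm | Not covered | Not required | Notes only, no AE CRF | Yes, in the row for any adverse event |

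Only the first row is treated alike by 13.4 and 13.5. The exception in 13.4 does not settle the others, because a site may read 13.5 and 13.7 as being that exception, and no later, non-immediate route is named. There is also an internal sign of conflict: if 13.5 alone governed, every reported SAE would be related, and the relatedness count in 13.4 would have no purpose.

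**Step 2. Listed complications (under-capture, same rule in both arms)**

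Inputs: the rates in 13.7, and 404 men, 202 per arm (SAP 1.4). Expected number = rate × men.

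- No overlap between men: 1% + 1% + 2% = 4%. 202 × 0.04 = 8.1 per arm; 404 × 0.04 = 16.2 in total.
- Complete overlap: the largest single rate, 2%. 202 × 0.02 = 4.0 per arm; 404 × 0.02 = 8.1 in total.
- Chance that the trial meets at least one listed laparotomy, 1 − (1 − p)^404: 98.3% at p = 1% (complete overlap of the two items) and above 99.9% at p = 2% (no overlap).

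So about 8 to 16 men are expected to have an event of this kind, and the waiver is almost certain to be used.

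For the row on any adverse event, the listed intra-operative items sum to 5.9% and the early post-operative items to 11.3%, together 17.2%. 404 × 0.172 = 69.5 men at most. This assumes no overlap, and it includes minor events such as seroma, syncope and wound infection. It sizes the footnote proposed below, not a count of major complications.

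**Step 3. Unlisted SAEs (possible imbalance)**

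The documents give neither a rate *r* nor a share *a* attributed to the technique. Read literally, 13.5 makes 202 × *r* × *a* events reportable in the NeuroSAFE arm and 0 in the control arm. Under assumed values, with the same true rate in both arms:

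| Assumed *r* | True number per arm | NeuroSAFE, *a* = 0 | *a* = 25% | *a* = 100% | Control |
|---|---|---|---|---|---|
| 2% | 4.0 | 0 | 1.0 | 4.0 | 0 |
| 5% | 10.1 | 0 | 2.5 | 10.1 | 0 |
| 10% | 20.2 | 0 | 5.1 | 20.2 | 0 |

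The control column is zero in every row. The difference runs from nothing to the full true count, and the documents do not say where in that range the trial would fall.

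**The case against.** The strongest reply is that 13.5 was meant only for expedited onward reporting. It cites guidance for non-CTIMP trials, and it speaks of reports that then go to sponsor and ethics. Much of the Protocol fits that reading. The causality scale in 13.3 includes categories for unrelated and unlikely events, which would have little use if only technique-related events were sent in. Section 13.7.2 observes SAEs from consent, and an event before surgery cannot result from NeuroSAFE. The assessment table in 7.4 has an adverse event row for all men. The Clavien-Dindo review in 13.4 has no stated limit by arm, expectedness or attribution, so much of the remedy already exists in outline. The available text also lacks a figure in 13.4 and perhaps a flow diagram in 13.6, and the SAE form, the CRFs and the iDMC charter are not in the documents. Finally, listed events should be in the notes, and the safety analysis is descriptive.

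Most of this stands as evidence of intention, and it makes actual loss of data less certain. It does not remove the conflict. The word limiting reports in 13.5 is unqualified and applies to the CTU itself, and no available text names a form that would bring a listed complication to the TMG.

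A reader might infer that laparotomies and similar events are captured unevenly by arm. The documents do not support that, because the waiver in 13.7 is identical in both arms. A reader might also infer that the reporting rule would produce a marked NeuroSAFE excess. That needs assumed rates and near-complete attribution to the technique, neither of which the documents supply.

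**Conclusion.** The concern holds as a conflict between stated rules. It does not show that safety data were lost, or that the NeuroSAFE arm is less safe. Two effects follow if sites apply 13.5 and 13.7 literally.

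- Listed complications are under-captured in both arms. For laparotomy and intensive care this is about 8 to 16 of 404 men, if the Protocol's rates apply to this trial. The Protocol assigns no Clavien-Dindo grade to these events.
- Unlisted SAEs may be imbalanced by arm, because no control-arm event can meet the wording of 13.5. The direction is towards more reported events in the NeuroSAFE arm. The size is unknown and may be nil.

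The primary and secondary efficacy analyses are unaffected. What is at risk is the reading of the table in SAP 4.5. The point merits a correction to the wording and an honest label on that table. Confidence is moderate, since forms or diagrams outside the available text may already provide wider capture.

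**What to change.** 1. In 13.5, state that the related-and-unexpected rule governs expedited onward reporting only.
2. In 13.5 and 13.7, state that all SAEs and all Clavien-Dindo grade 3+ complications, from surgery to 90 days, are recorded on a CRF in both arms, whether or not expected and whatever the attribution. Keep the blinded TMG grading and the existing rule for deaths.
3. Build the SAP 4.5 table from these records. Add a footnote to the row for any adverse event saying that lower-grade events listed in 13.7 needed no CRF.
4. For men already past 90 days, complete the records from the medical notes where feasible. Where that is not done, state with the table that capture was limited by 13.5 and 13.7 and that the arms are not comparable for unlisted SAEs.

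**Cost.** The wording changes and the footnote cost little, and no extra expedited reporting is needed. The SAP describes recruitment in the past tense, so the retrospective step may be the main one. The completed forms would be few, but finding the events could mean checking up to 404 sets of notes across five sites. If the existing CRFs already collect these events, steps 1 and 3 and a cross-reference are enough.

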### 13.6 Flow of SAE Reporting

SAE Reporting:  
Please email the completed SAE form to: [[contact]](mailto:[contact])

## 13.7 Expected Adverse Events

The following are expected adverse events following a radical prostatectomy with their corresponding likelihoods (31-34). These should be recorded in the patient's medical records but do not need an Adverse Event CRF to be submitted. These will be recognised as expected for trial treatment.

### **Expected adverse events:**

#### **Intra-operative**

Bleeding – (requiring transfusion) - 1%  
Visceral injury requiring laparotomy – 1%  
Vascular injury requiring laparotomy – 1%  
Cardiac event (Myocardial infarction 0.1%, Atrial Fibrillation 1.6%, syncope 1.2%).

#### **Early post-operative**

Wound related problems; infection (2%), incisional hernia (2%)  
Thromboembolic event (deep vein thrombosis or pulmonary embolus 0.8%)  
Lymphoedema – 1% (higher incidence when eLND performed)  
Anaesthetic problems requiring admission to intensive care unit (2%)  
Gastrointestinal; ileus/damage to bowel requiring temporary colostomy (0.5%)  
Seroma – 1%  
Urethral Stricture – 2%

#### **Expected longer term outcomes or side effects of surgery**

Urinary incontinence (temporary) –100%  
Erectile dysfunction – (up to 100%)  
Long term urine leak – 10%  
Adjuvant therapies (including radiotherapy and ADT) – 30%

### 13.7.1 Notification of Death

As with all major surgery there is also a risk of death. The risk of death with either of these surgical interventions is thought to be less than one in a hundred. Any deaths including deaths unrelated to the treatment will be recorded on the CRF/database.

### 13.7.2 Period of observation

For the purpose of this trial, the period of observation of serious adverse events extends from consent to 90 days post op as it unlikely any SAEs past this point will be related to surgery. This will reduce site reporting workload. Trial follow up should continue according to schedule once the SAE is resolved, if applicable. The trial will, however, continue to collect death SAEs throughout per section 13.7.1.

## 14 ETHICAL CONSIDERATIONS

The Chief Investigators will take primary responsibility for the conduct of the trial in accordance with the World Medical Association Declaration of Helsinki and subsequent amendments, and the conduct will conform to ICH GCP guidelines and the Research Governance Framework Guidelines.

**Subject Information and Informed Consent:** The patient's consent to participate in the trial should be obtained after a full explanation has been provided of the procedures to be given. All subjects must sign and personally date an approved informed consent after having received detailed written and verbal information about the reason, nature and possible risks associated with the research program. Patients should be given sufficient time after being given the trial patient information sheet to consider and discuss participation in the trial with family and friends. Patients will always be asked to sign a consent form. One copy will be given to the patient, one copy will be kept with patient's hospital notes and one copy should be kept in the local investigator site file.

The subject must be made aware and agree that personal information may be scrutinized during monitoring and audit by competent authorities and properly authorized persons. However, personal information will be treated as strictly confidential and will not be publicly available.

The right of the patient to refuse to participate in the trial without giving reasons must be respected. After the patient has entered the trial, the clinician must remain free to manage the patient however he/she feels fit to suit the best interest of the patient, regardless of the protocol. Similarly, the patient must remain free to withdraw from the trial at any time without giving reasons and without prejudicing any further treatment or the standard of care received.

An Institutional Review Board and/or an Independent Ethics Committee must approve the protocol, the patient information sheet, the content of the informed consent form and any promotional materials used for the recruitment of subjects before the accrual of any patients. If legally required, the protocol and informed consent must be submitted to the country regulatory authorities.

